5.5 Duration of Follow Up

Patients will be followed for 100 days based on 5 half lives after removal from study or until death, whichever occurs first. Patients removed from study for unacceptable adverse event(s) will be followed until resolution or stabilization of the adverse event. Patients who complete all protocol therapy (46 doses), without disease progression or unacceptable toxicity will continue to be followed until disease progression or the initiation of a new anticancer therapy.

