 - a: Laboratory testing prior to each dose: Within 72 hrs prior to re-dosing to include CBC w/ differential, LFTs, BUN or serum urea level, creatinine, Ca, Mg, Na, K, Cl, LDH, Glucose, amylase, and lipase. TSH will be collected at screening and repeated every 6 weeks unless clinically indicated. Reflexive Free T4 and Free T3 will be collected at screening and repeated when clinically indicated.
 - b: A serum or urine pregnancy test is required at baseline for women of childbearing potential.
 - c: Off-study evaluation. AE assessment will be performed at 100 days following last dose of study drug. This may be done by phone. Patients who complete all planned protocol therapy (46 doses), will continue to be monitored for tumor measurements beyond completion of treatment until disease progression or the initiation of a new anticancer therapy.
 - d: Pre/post tumor biopsies will be required for all participants.
 - e: Pre-study tumor biopsy to be performed after eligibility is confirmed and patient is registered on study and prior to first dose of combination therapy with nivolumab + ipilimumab .
 - f: Peripheral blood will be drawn prior to study drug infusion for the first 4 cycles to assess changes in immune function as per section 9.2. Samples will also be drawn within 7 days of an objective response, and at off-study.
 - g: Post-treatment biopsy will be performed at approximately week 4-6 (+/- 7 days)
 - h: Archival tissue specimen will be collected if available. This is not required prior to study drug dosing.
 - i: Testing for human immunodeficiency virus (HIV) or known acquired immunodeficiency syndrome (AIDS), hepatitis B virus surface antigen (HBV sAg) and hepatitis C virus ribonucleic acid (HCV antibody) indicating acute or chronic infection. These viral serologies may be performed within 28 days of registration.
 - j: Tumor assessments are repeated every 8 weeks (+/- 2 days) and should continue as per protocol regardless of dosing interruptions.
 - k: For patients with a history of congestive heart failure (CHF) or at risk because of underlying cardiovascular disease or exposure to cardiotoxic drugs, EKG and ECHO will be collected as clinically indicated.
 - l: For patients with evidence of CHF, myocardial infarction (MI), cardiomyopathy, or myositis, cardiac evaluation including lab tests and cardiology consultation (EKG, CPK, troponin levels, ECHO) will be conducted as clinically indicated.

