11 MEASUREMENT OF EFFECT

11.1 Antitumor Effect – Solid Tumors

For the purposes of this study, patients should be re-evaluated for response every 8 weeks (+/- 2 days). In addition to a baseline scan, confirmatory scans should also be obtained at least 4 weeks following initial documentation of objective response.

Response and progression will be evaluated in this study using the new international criteria proposed by the revised Response Evaluation Criteria in Solid Tumors (RECIST) guideline (version 1.1) [Eur J Ca 45:228-247, 2009]. Changes in the largest diameter (unidimensional measurement) of the tumor lesions and the shortest diameter in the case of malignant lymph nodes are used in the RECIST criteria.

All patients who receive at least one dose of nivolumab and ipilimumab each will be included in the toxicity analysis. This includes participants who receive study drug and are ultimately deemed ineligible.

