11.1.6 Progression-Free Survival

Progression-Free Survival will be evaluated as a secondary objective. PFS is defined as the duration of time from start of treatment to time of progression or death, whichever occurs first.

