13.4 Analysis of Secondary Endpoints

COHORT A – SECONDARY ENDPOINTS

We will also assess toxicity in patients with ULMS treated with nivolumab. Among the first phase of 12 patients, there is at least 58% probability of observing one or more rare (7% true probability) events, and 83% probability of observing toxicities that have a true occurrence of at least 15%. Among the total cohort of 37 patients, there is at least 85% probability of observing one or more rare (5% true probability) events, and 95% probability of observing toxicities that have a true occurrence of at least 8%. With 37 treated patients, the maximum width of a 90% two-sided exact binomial confidence interval for any estimated adverse event proportion will be no wider than $\pm 14\%$.

Rate of Progression-free survival at 12 weeks with a null hypothesis of 20% and an alternative hypothesis of 40% at 12 weeks will be investigated. Patients lost to follow-up or deaths within 12 weeks will be counted as failures. The overall power for overall progression-free rate at 12 weeks is 87%, using the exact binomial distribution. The

operating characteristics of this design are calculated using a one-sided exact test with 10% type I error.

COHORT B – SECONDARY ENDPOINTS

Toxicity: Among the first phase of 8 patients, there is at least 57% probability of observing one or more rare (10% true probability) events, and 73% probability of observing one or more toxicities that have a true occurrence rate as low as 15%. Among the total cohort of 25 patients, there is at least 84% probability of observing one or more rare (7% true probability) events, and 93% probability of observing toxicities that have a true occurrence of at least 10%. With 25 treated patients, the maximum width of a 90% two-sided exact binomial confidence interval for any estimated adverse event proportion will be no wider than $\pm 18\%$.

Rate of Progression-free survival at 6 months with a null hypothesis of 18% and an alternative hypothesis of 40% at 6 months will be investigated. Patients lost to follow-up or deaths within 6 months will be counted as failures. The overall power for overall progression-free rate at 6 months is 85%, using the exact binomial distribution. The operating characteristics of this design are calculated using a one-sided exact test with 10% type I error.

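### Tumor scans after stopping are required only for patients who complete all doses, so in Cohort B the 6-month progression status of early stoppers may go unobserved and the PFS rate is biased downward

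*Combined protocol and SAP*

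**What the plan says.** **Follow-up after removal.** Section 5.5 sets the general limit: "Patients will be followed for 100 days based on 5 half lives after removal from study or until death, whichever occurs first". For toxicity removals it adds: "Patients removed from study for unacceptable adverse event(s) will be followed until resolution or stabilization of the adverse event". That sentence concerns the event, not the tumor. Only patients who complete all 46 doses "will continue to be followed until disease progression or the initiation of a new anticancer therapy".

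**Calendar (section 10, Cohort B).** Footnote c says that the same completers "will continue to be monitored for tumor measurements beyond completion of treatment until disease progression or the initiation of a new anticancer therapy". It makes the 100-day contact an adverse-event assessment that may be done by phone. The table marks one tumor measurement in the Off Study column. Footnote j keeps the 8-weekly scans going through dosing interruptions and does not mention permanent discontinuation.

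**Removal.** Section 5.6 lists adverse events, withdrawal and inability to follow the protocol beside progression, so removal without progression is foreseen.

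**Endpoints.** Section 11.1.6: "PFS is defined as the duration of time from start of treatment to time of progression or death, whichever occurs first". Section 13.4 tests the 6-month progression-free rate in Cohort B (18% against 40%, one-sided exact test at 10%, power 85%) and adds: "Patients lost to follow-up or deaths within 6 months will be counted as failures". On response, section 11.1 says that "confirmatory scans should also be obtained at least 4 weeks following initial documentation of objective response".

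**The concern.** PFS runs to progression or death and does not end when treatment stops, but the scans that would show progression do end then, unless the patient has had every planned dose. The completers' provision cannot help the 6-month endpoint, because completing Cohort B treatment takes 4 × 3 + 46 × 2 = 104 weeks. The one other provision for documenting progression after stopping, in section 11.1.4.3, covers only symptomatic deterioration.

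The plan also does not say whether a patient whose scheduled follow-up simply ended, or who stayed in follow-up without a scan, is lost to follow-up in the sense of 13.4. Two analysts could code that patient differently. If the patient is coded as a failure, the 6-month rate mixes progression with tolerability. The risk is then a false negative: an active combination could look less active than it is. A scan that was never taken cannot be recovered at analysis.

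**Working it through.** **1. Who is affected.** Six months is about 182 to 183 days. The 100-day follow-up ends before that only if removal comes before day 182 − 100 = 82, or 183 − 100 = 83. The combination phase lasts 4 × 21 = 84 days, so this covers nearly all removals during it. (Footnote c counts the 100 days from the last dose and section 5.5 from removal; the same subtraction applies to either start.) A patient removed later, but before the landmark, is still in follow-up at 6 months and also has no required scan after the Off Study one. On the 8-weekly schedule the scans around the landmark fall at weeks 24 and 32. A patient whose 6-month status is already documented at removal is unaffected.

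**2. The plan's own figure.** Inputs from 13.2 and 13.4: n = 25, p0 = 0.18, p1 = 0.40, one-sided 10%. The rule is the smallest r with P(X ≥ r | 25, 0.18) ≤ 0.10.

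- r = 7: type I error 0.149, too large.
- r = 8: type I error 0.066, power P(X ≥ 8 | 25, 0.40) = 0.846.

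This agrees with the stated 85%.

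**3. Effect of counting unscanned patients as failures.** Let d be the share of patients who stop before 6 months without progression, have no later scan and are coded as failures. Assume that d is independent of true 6-month status. The observed rate is then p(1 − d), with the cutoff still at 8 of 25. The documents give no value of d for this population. As a range, section 2.4 cites discontinuation for adverse events of 3% to 10% in a lung cancer trial of the combination, and 36.4% in the combination arm of a melanoma trial.

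| d | Rate if true 40% | Power | Actual type I error |
|---|---|---|---|
| 0 | 40.0% | 84.6% | 6.6% |
| 3% | 38.8% | 81.6% | 5.7% |
| 5% | 38.0% | 79.3% | 5.1% |
| 10% | 36.0% | 72.9% | 3.9% |
| 36.4% (extreme bound) | 25.4% | 29.1% | 0.5% |

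In patients, 3% to 10% of 25 is 0.75 to 2.5.

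**4. Response.** The Cohort B two-stage design (at least 1 of 8, then at least 3 of 25; 5% against 30%) reproduces: type I error 9.4%, power 93.8%, early stopping under the null 66.3%, against the stated 9%, 94% and 66%. Suppose a share k of true responses went unconfirmed. The chance of passing the first stage is 1 − (1 − 0.30(1 − k))^8:

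- k = 0: 94.2%
- k = 3%: 1 − 0.709^8 = 93.6%
- k = 10%: 1 − 0.73^8 = 91.9%

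Overall power at k = 10% is 91.0%. Nothing in the documents links k to the discontinuation rate, so these values are illustrative.

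**The case against.** **A status is already assigned.** A reader might infer that early stoppers have no 6-month PFS status at all. The documents do not support that: 13.4 supplies a default, failure, for patients lost to follow-up. Failure imputation is a legitimate prespecified choice in a single-arm landmark test, and it lowers the type I error. This stands. What remains is that the status is imputed where it could be observed, that the reach of the rule is unclear, and that power is lost.

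**The 36.4% rate does not transfer.** A reader might infer that power could collapse to 29.1%. That rate comes from a different tumor and different doses of both drugs. It is not restricted to stops before 6 months or without progression. Section 5.7 also lets some patients who stop the combination continue single-agent nivolumab on study, where scanning goes on. It serves only as an extreme bound.

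**Confirmation is already called for.** A reader might infer that the primary endpoint is at serious risk, since the first stage turns on a single response. But section 11.1 asks for the confirmatory scan without an on-treatment condition, 4 weeks fits well inside 100 days, and the Off Study scan can confirm if it falls late enough. A wrongful first-stage stop would need a sole responder among eight, removal between first response and confirmation, and no qualifying scan. This objection largely stands. The remaining gap is that no schedule after removal ensures the confirmatory scan is done. For example, after a first response at week 8 and a stop at week 10, an off-study scan at the stop would be only 2 weeks after first response.

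**Conclusion.** The gap is real and is established by the text: no section schedules a scan after the Off Study one for a patient removed early without progression, although PFS is defined to progression or death. The consequence is a conservative downward bias in a secondary endpoint. If 3% to 10% of patients are affected, the loss is about 3 to 12 points of power (84.6% to between 81.6% and 72.9%), with actual type I error falling to between 5.7% and 3.9%.

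These figures assume that affected patients are coded as failures and that being affected is unrelated to true 6-month status. The 3% to 10% range is borrowed from another tumor and set of schedules; it is not a forecast for this trial. The effect on the first-stage response decision is about 0.6 to 2.3 points over the same range and does not drive the conclusion. This is a should-fix point.

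**What to change.** - **Section 5.5 and Cohort B footnote c:** continue the 8-weekly tumor measurements for any patient who stops treatment without RECIST progression, until progression, new anticancer therapy, death or withdrawal of consent. This extends the rule that completers already have.
- **Section 5.5:** state that the 100-day limit applies to adverse-event follow-up, and give it the same starting point as footnote c.
- **Section 11.1:** state that the confirmatory scan applies even if treatment has stopped.
- **Section 13.4:** keep the failure rule for patients whose 6-month status remains unobtainable, and say explicitly that this is whom it covers.

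The cost is protocol wording, a few more routine scans and somewhat longer follow-up in the minority who stop early. The sample size and decision rules do not change. The change has to be made prospectively.

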5.6 Criteria for Removal from Study

Patients will be removed from study when any of the applicable criteria, including progressive disease as per section 5.9, adverse events, patient withdrawal or inability to follow study protocol as listed in Section 5.4. The reason for study removal and the date the patient was removed must be documented in the Case Report Form.

5.7 Criteria to Resume Treatment

Management of adverse events is summarized in section 6 and may include holding of nivolumab and ipilimumab, and/or the use of steroids for the management of immune related AEs.

If drug administration is held until the next scheduled time point, please continue to count weeks/doses. If patients must be delayed due to toxicity, all assessments can be obtained with the modified treatment dose schedule as noted in this section.

Some patients may continue to benefit from treatment, maintaining or improving responses after progression including those treated with steroids.

Restarting nivolumab may be considered in patients who experience grade 2 events and some grade 3 events (skin rash and thyroiditis). Because of this, stopping treatment and starting steroids earlier, as per section 6, to obtain resolution with the possibility for restarting rather than waiting for higher grade events is encouraged.

For non-autoimmune or non-inflammatory events patients may resume treatment with study drug when the drug-related AE(s) resolve to Grade ≤ 1 or baseline value, with the following exceptions:

- Evaluation to exclude any additional immune mediated events endocrine, GI, and liver / pancreas function as clinically indicated must be made prior to restarting.
- Non-drug-related toxicity including hepatic, pulmonary toxicity, diarrhea, or colitis, must have resolved to baseline before treatment is resumed.

If the criteria to resume treatment are met, the patient should restart treatment no sooner than the next scheduled time point per protocol. However, if the treatment is delayed past the next scheduled time point per protocol the treatment should resume at the earliest convenient point that is within the six week delay period.

For protocols using combination nivolumab/Ipilimumab for the initial induction period patients with grade 2 or 3 events requiring discontinuation of treatment with the combination, the PI may consider continuing treatment with single agent nivolumab at the same dose when the event resolves to baseline. However, patients with renal, CNS, or pulmonary toxicity must be removed from study.

For patients treated with corticosteroids:

For patients treated with high dose steroids with nivolumab/Ipilimumab, toxicity must resolve to baseline within 8 weeks of treatment.

Patients should be off steroids for at least 2 weeks with no recurrence or new events. New immune related events or exacerbation of existing events during steroid treatment or taper suggest the presence of ongoing immune activation and should require permanent discontinuation of nivolumab.

Grade 2 events must resolve to grade ≤ 1 before considering retreatment.

All patients treated with steroids for grade ≥ 2 events should have nivolumab held until resolution to grade ≤ 1 for at least 2 weeks following complete removal from steroid treatment except for maintenance replacement doses for adrenal insufficiency (preferably no greater than 10mg prednisone equivalent daily).

All patients treated with steroids for grade ≥ 3 events should have nivolumab discontinued. Patients with grade 3 thyroiditis and skin rash may continue therapy as for grade 2 events with resolution and stable replacement treatment.

Patients with hepatitis, pancreatitis, pneumonitis, and colitis are at risk for exacerbation with retreatment if there is residual inflammation and should resolve to Grade 0 or baseline before retreatment. Baseline can mean the initial grade *i.e.* grade <1 where permitted on study.

Patients with thyroiditis or hypopituitarism who are stable as above may be restarted with replacement hormones including thyroid hormone and physiologic doses only of corticosteroids. Please note that grading and for hypophysitis with symptoms of headache, visual or neurologic changes or radiologic evidence of pituitary enlargement and other CNS events such as aseptic meningitis or encephalitis should be considered grade 3 events.

New immune related events or exacerbation of existing events during steroid treatment or taper suggest the presence of ongoing immune activation and should require permanent discontinuation of nivolumab.

A patient who is treated with steroids, evaluated, and found to not have an autoimmune or inflammatory event requiring steroid treatment, may be restarted if asymptomatic off steroids for 2 weeks and other restarting criteria are met.

Prior to starting corticosteroids or hormone replacement for any reason, appropriate endocrine

testing including cortisol, ACTH, TSH and T4 must be drawn if clinically feasible to document baseline function and distinguish the pituitary from peripheral organ dysfunction and later from steroid (or thyroid) treatment associated ACTH (or TSH) suppression. Steroids should be started prior to obtaining results based on clinical indications.

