5.4 Duration of Therapy

In the absence of treatment delays due to adverse event(s), treatment may continue for up to 46 doses in Cohort A or until one of the following criteria applies. In Cohort B, treatment may continue for up to 4 doses of combination therapy (nivolumab + ipilimumab), and up to 46 doses of nivolumab monotherapy after the combination therapy, or until one of the following criteria applies:

- Disease progression, as per section 5.9
- Intercurrent illness that prevents further administration of treatment,
- Any patients who require additional immune suppressive treatment beyond steroids should go off study treatment
- Unacceptable adverse event(s) which include the following (see also section 6 and

specific algorithms in Appendix E):

- Any grade 2 drug-related uveitis or eye pain or blurred vision that does not respond to topical therapy and does not improve to Grade 1 severity within the re-treatment period OR requires systemic treatment
- Patients requiring > two dose delays for the same type of event should go off protocol therapy.
- Any adverse event, laboratory abnormality, or intercurrent illness which, in the judgment of the investigator, presents a substantial clinical risk to the subject with continued study drug dosing
- Any dosing interruption lasting >6 weeks, with the following exceptions:
- Patients being tapered after high dose corticosteroids over one month followed by a two-week observation period will be allowed an additional two weeks to restart treatment (a maximum eight week interruption).
- Dosing interruptions >6 weeks that occur for non-drug-related reasons may be allowed if approved by the Investigator. Prior to re-initiating treatment in a subject with a dosing interruption lasting >6 weeks, the Principal Investigator must be consulted.
- Grade 3 drug-related autoimmune or inflammatory events including uveitis, pneumonitis, diarrhea, colitis, neurologic adverse events, hypersensitivity reaction, or infusion reaction of any duration requires discontinuation except as noted below:
- Any other grade 3 non-skin, drug-related AE lasting >7 days including fatigue.
- Any grade 3 or 4 drug-related laboratory abnormality or electrolyte abnormality, not associated with underlying organ pathology, that does not require treatment except for electrolyte replacements **does not** require treatment discontinuation.

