6 DOSING DELAYS/DOSE MODIFICATIONS

Dose delays for nivolumab and ipilimumab for adverse events are described below. There are no dose reductions of nivolumab or ipilimumab allowed. See section 5.6 for guidelines regarding resumption of nivolumab and ipilimumab following dose delays.

Please refer to the Nivolumab Investigator Brochure, Ipilimumab Investigator Brochure or Appendix B to the protocol for toxicity management algorithms which include specific treatment guidelines. These algorithms should be followed unless there are specific clinical circumstances which the treating physician indicates variations or alternative treatment is needed.

Evaluation of possible AEs should occur early, with early withholding of drug, and appropriate treatment as indicated in the management tables and following event specific guidelines. In some cases, nivolumab and ipilimumab may be resumed as per section 5.6

| ALL OTHER EVENTS* | Management/Next Dose for Nivolumab and combination Nivolumab/ipilimumab |
|---------------------------------|--|
| ≤ Grade 1 | No change in dose |
| Grade 2 | Hold until ≤ Grade 1 OR baseline (exceptions as noted below); Evaluate and continue at investigator discretion |
| Grade 3 | Off protocol therapy (exceptions as noted below) |
| Grade 4 | Off protocol therapy |

* **Not agent related**, or agent related non-immunologically mediated

Recommended management: As clinically indicated

| ALL OTHER EVENTS** | Management/Next Dose for Nivolumab and combination Nivolumab/ipilimumab |
|----------------------------------|---|
| ≤ Grade 1 | No change in dose |
| Grade 2 | Hold until ≤ Grade 1 OR baseline* When resolved < or following steroids resume at same dose level . |
| Grade 3 | Off protocol therapy (exceptions noted in 5.4) |

| ALL OTHER EVENTS* | Management/Next Dose for Nivolumab and combination Nivolumab/ipilimumab |
|---|--|
| Grade 4 | Off protocol therapy |
| ** immunologically mediated | |
| Recommended management: As clinically indicated | |

- Any grade 2 drug-related uveitis or eye pain or blurred vision that does not respond to topical therapy and does not improve to Grade 1 severity within the re-treatment period OR requires systemic treatment should go off protocol treatment.
- Any adverse event, laboratory abnormality, or intercurrent illness which, in the judgment of the investigator, presents a substantial clinical risk to the subject with continued study drug dosing should go off protocol treatment.

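### Cohort B stopping rules contradict each other for some Grade 3 immune-mediated events: colitis between 5.4 and Section 6, and the 5.7 step-down to nivolumab alone against 5.4 and Section 6

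*Combined protocol and SAP*

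**What the plan says.** **Section 5.7, step-down.** For protocols that start with the combination, after a Grade 2 or 3 event that ends it, "the PI may consider continuing treatment with single agent nivolumab at the same dose when the event resolves to baseline". One limit by organ follows: "However, patients with renal, CNS, or pulmonary toxicity must be removed from study".

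**Section 5.7, restart sentence.** A few paragraphs above the step-down, the same section names skin rash and thyroiditis as the Grade 3 events after which restarting nivolumab may be considered.

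**Section 5.7, steroid rule.** "All patients treated with steroids for grade ≥ 3 events should have nivolumab discontinued". The exception follows: "Patients with grade 3 thyroiditis and skin rash may continue therapy as for grade 2 events with resolution and stable replacement treatment".

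**Section 5.4.** Treatment ends for certain events, including Grade 3 "drug-related autoimmune or inflammatory events including uveitis, pneumonitis, diarrhea, colitis, neurologic adverse events, hypersensitivity reaction, or infusion reaction of any duration requires discontinuation". Exceptions are listed below that rule, for some laboratory and electrolyte abnormalities and for some amylase or lipase rises. The step-down is not among them.

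**Section 6.** The tables concerned are headed for both nivolumab and the combination.
- Liver function, Grade 3: off protocol therapy.
- Other immunologically mediated events, Grade 3: "Off protocol therapy (exceptions noted in 5.4").
- Diarrhea/colitis, Grade 3: hold, then resume at the investigator's discretion after recovery to Grade 1 or baseline.

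The opening text of Section 6 refers twice to 5.6 for resumption rules. Section 5.6 is the removal section; the resumption rules are in 5.7.

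**Appendix B, hepatic footnote.** Immuno-oncology therapy may be delayed instead of stopped when AST/ALT is at most 8 times and bilirubin at most 5 times the upper limit of normal.

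**The concern.** Whether to give a checkpoint inhibitor again after a Grade 3 immune-mediated event is a safety decision, and a treating physician needs one answer. Here a physician can follow one section and breach another.

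For colitis, the two sections that should agree say stop and resume. For hepatitis and the residual immune-mediated category, the step-down as worded reaches patients whom three other rules stop. The protocol itself notes the hazard: patients with hepatitis, pancreatitis, pneumonitis or colitis "are at risk for exacerbation with retreatment if there is residual inflammation and should resolve to Grade 0 or baseline before retreatment".

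Toxicity of the combination is a secondary objective (Section 1.2). Unclear continuation rules therefore also blur what exposure the toxicity results describe.

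**Working it through.** No sample size, power or error rate is involved, so the check sets the rules side by side and follows the cross-references.

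**Step 1. Apply each rule to a Cohort B patient whose drug-related Grade 3 event ended the combination and has returned to baseline.**

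| Event | 5.7 step-down | 5.7 restart sentence | 5.4 | 5.7 steroid rule | Section 6 |
|---|---|---|---|---|---|
| Diarrhea/colitis | may continue nivolumab | not named | stop | stop if steroids given | may resume |
| Immune-mediated hepatitis | may continue nivolumab | not named | stop | stop if steroids given | off protocol therapy |
| Other immune-mediated events (residual row) | may continue nivolumab | not named | stop | stop if steroids given | off protocol therapy, 5.4 exceptions only |

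The first row conflicts whatever the step-down means, because 5.4 and Section 6 disagree directly. In the other two rows only the step-down, read literally, points towards continuing. For liver events the Appendix B footnote adds a further instruction. The visible text does not tie it to a grade, and the algorithm figure is not shown.

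**Step 2. Remove the events for which the step-down creates no conflict.**
- Renal, CNS and pulmonary toxicity: excluded by the step-down itself.
- Skin rash and thyroiditis: allowed to continue by 5.7 and by the closing text of Section 6.
- Hypopituitarism: "Patients with thyroiditis or hypopituitarism who are stable as above may be restarted with replacement hormones".
- Laboratory-only abnormalities: exempted in 5.4 and Section 6 under stated conditions.
- Steroid-treated Grade 3 events other than rash and thyroiditis: 5.7 itself says to stop nivolumab, so a site that follows the whole section stops.

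Mainly Grade 3 hepatitis and other immune-mediated events that were not given steroids and are not laboratory-only remain.

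**Step 3. Look for text that ranks the rules.**
- 5.7 opens by saying that Section 6 summarizes adverse event management.
- The Section 6 immune-mediated row takes its exceptions from 5.4, and 5.4 does not list the step-down.
- 5.4 refers the reader to Section 6, whose colitis row contradicts it.
- Section 6 sends resumption to 5.6, which refers back to 5.4.
- Section 6 sends patients on high-dose steroids to 5.7, which holds both the permission and the stop rule.

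For hepatitis and the residual category, most of these references lead to stopping, but no sentence says that the step-down yields. For colitis they lead in a circle.

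**Step 4. Bound the period.** The step-down concerns events that end the combination, which is planned for 4 cycles × 3 weeks = 12 weeks (Section 5.1.2). Section 5.4 also limits interruptions to 6 weeks, or 8 weeks after a high-dose steroid taper, apart from approved non-drug-related delays. The colitis conflict is not confined to those 12 weeks, because the table also covers nivolumab alone.

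**The case against.** The best defence is that 5.7 should be read as a whole. The restart sentence names the Grade 3 events after which nivolumab may resume, the steroid rule and its exception agree with it, and the step-down is permissive where 5.4 is mandatory. On that reading the step-down covers Grade 2 events and the named Grade 3 exceptions. This is the most natural reading, and it stands as a guide to intent. It does not settle the text: the step-down speaks of Grade 2 or 3 events and then lists its own exclusions, which implies that other Grade 3 events are included. Nor does it touch the colitis conflict.

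The safeguards also stand. Resolution to baseline, the interruption limits and a decision by the PI reduce the harm. They do not tell the decision-maker which rule applies.

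A reader might infer more than the documents support:
- **That nothing in the protocol limits the step-down.** The restart sentence and the steroid rule both do.
- **That two sites would treat the same patient in opposite ways.** The step-down is the PI's decision, and the protocol does not say which PI. Section 5.4 separates the Investigator from the Principal Investigator, and Section 12.1 separates the Protocol Principal Investigator from site investigators, while Section 12.1.2 speaks of PIs at the site. If the Protocol Principal Investigator decides, there is one decision-maker.
- **That Grade 3 adrenal insufficiency belongs with hepatitis.** The step-down needs a return to baseline, which a patient on replacement may not reach, and Section 6 exempts short endocrine steroid tapers from 5.7 management. That limb is too thin to carry.
- **That a frequency can be taken from Section 2.4.** The 10% hepatic rate there is for Grade 3 or 4 events in one lung-cancer arm on a different schedule, and it does not separate events that resolved or were managed without steroids.

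**Conclusion.** The contradiction is real but narrow. Grade 3 diarrhea/colitis has opposite instructions in 5.4 and Section 6. The step-down is worded more widely than 5.4, the steroid rule, the restart sentence and the Section 6 Grade 3 liver and other-immune rows allow. After the exemptions, the unresolved step-down group is mainly Grade 3 hepatitis and other immune-mediated events without steroid treatment.

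The size of that group cannot be stated, because the documents give no rate for it under this regimen. The response analysis is unaffected: Section 13.6.2 keeps eligible patients in the main analysis even when the treatment schedule was wrong. The consequence is for safety conduct and for how clearly the toxicity results can be read.

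The conclusion rests on the visible text. The Appendix B algorithm figures are not shown and might bear on liver events or colitis. It should be fixed, at moderate priority.

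**What to change.** 1. In 5.7, limit the step-down to Grade 2 events and to the Grade 3 events already allowed to resume: rash, thyroiditis and the stated laboratory exceptions. Add that it does not override 5.4, the steroid rule or Section 6.
2. Change the Section 6 Grade 3 diarrhea/colitis row to agree with 5.4.
3. State whether the Appendix B hepatic footnote applies to Grade 3 liver events.
4. Correct the two resumption pointers at the start of Section 6 from 5.6 to 5.7.

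If the sponsor does intend the step-down for Grade 3 hepatitis or other immune-mediated events, it should instead be listed as an explicit exception in 5.4, in the steroid rule and in the affected Section 6 rows.

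The cost is an amendment to the wording, with no extra patients or procedures. The downside of the change in items 1 to 4 is that a few patients whose Grade 3 event resolved would lose access to nivolumab alone.
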